10.2.3 Other study parameters

Descriptive statistics will be performed for demographics collected at baseline.

10.2.4 Interim analysis

Not applicable.

11. ETHICAL CONSIDERATIONS

11.1 Regulation statement

The investigator will ensure that this study is conducted in full compliance with the principles of the "Declaration of Helsinki" (as amended in Seoul, Tokyo, Venice, Hong Kong, South Africa and Edinburgh), ICH guidelines, or with the laws and regulations of the country in which the research is conducted, whichever affords the greater protection to the study subject.

11.2 Recruitment and consent

Eligible patients will be asked for participation by their treating physician or a committed research nurse. A patient information folder with extensive information will be handed out to possible subjects. It is the responsibility of the investigator to obtain written informed consent from each individual participating in this study after adequate explanation of the aims, methods, objectives, and potential hazards of the study and prior to undertaking any study-related procedures. The investigator must utilize an IEC-approved consent form for documenting written informed consent. Each informed consent will be appropriately signed and dated by the subject and the persons obtaining consent.

An oral summary of the most important topics (e.g. the burden and the right to withdraw without consequences) will be given before screening, including time for additional questions. If necessary, additional time to (re)consider participation will be provided.

11.3 Objection by minors or incapacitated subjects

Not applicable.

11.4 Benefits and risks assessment, group relatedness

Benefits associated with participating in this study are that patients and their treating physician get insight into the effect of flushing after HIPEC on tumour exposure.

Patients who participate in the study will receive standard treatment conform local protocol. Therefore the risk for participation in this study is regarded negligible. Collection of peritoneal fluid, blood, and wound exudate samples do not put patients at risk or interfere with standard treatment. In the group of patients receiving HIPEC with flushing two 5-cm diameter non-tumour peritoneal tissue samples will be taken prior to and at the end of flushing. In the group of patients receiving HIPEC without flushing one 5-cm diameter non-tumour peritoneal tissue sample will be taken prior to abdominal closure. Compared to the complexity and amount of cytoreduction that is performed during surgery this can be considered as a minor procedure.

11.5 Compensation for injury

The sponsor/investigator has a liability insurance which is in accordance with article 7 of the WMO.

The sponsor (also) has an insurance which is in accordance with the legal requirements in the Netherlands (Article 7 WMO). This insurance provides cover for damage to research subjects through injury or death caused by the study.

The insurance applies to the damage that becomes apparent during the study or within 4 years after the end of the study.

11.6 Incentives

Subjects will receive no compensation for participating in the study.

12. ADMINISTRATIVE ASPECTS, MONITORING AND PUBLICATION

12.1 Handling and storage of data and documents

The investigator must assure that subjects' anonymity will be strictly maintained and that their identities are protected from unauthorized parties. Blood samples for PK analysis will be identified by study name, patient number, date and time of sampling and sample code. The medical record and other source documents are only accessible by the medical staff of the clinical research centre, the investigator and monitor. CRFs do not contain identifiable information and will be coded with randomization numbers only. Information and study files that are necessary for the evaluation of the research are stored anonymously and the identification key will not be accessible by unauthorized parties.

12.2 Monitoring and Quality Assurance

The monitor will be a staff member at the Pharmacy at the Radboud University Nijmegen Medical Centre. The monitor will work independently and has no involvement in the set up of the study, the conduct of the study and interpretation of the results.

Monitoring consists of:

- check essential documents at the site
- check eligibility of subjects prior to study start
- monitoring for completeness and correctness of the source documents
- monitoring of the data in the workbook, and transfer of data from source documents to the CRF
- write monitoring reports

12.3 Amendments

Amendments are changes made to the research after a favourable opinion by the accredited METC has been given. All amendments will be notified to the METC that gave a favourable opinion.

Non-substantial amendments will not be notified to the accredited METC and the competent authority, but will be recorded and filed by the sponsor.

12.4 Annual progress report

The sponsor/investigator will submit a summary of the progress of the trial to the accredited METC once a year. Information will be provided on the date of inclusion of the first subject, numbers of subjects included and numbers of subjects that have completed the trial, serious adverse events/ serious adverse reactions as consequence of the additional sample collection, other problems, and amendments.

12.5 Temporary halt and (prematurely) end of study report

The investigator/sponsor will notify the accredited METC of the end of the study within a period of 8 weeks. The end of the study is defined as the last patient's last visit.

The sponsor will notify the METC immediately of a temporary halt of the study, including the reason of such an action.

In case the study is ended prematurely, the sponsor will notify the accredited METC within 15 days, including the reasons for the premature termination.

Within one year after the end of the study, the investigator/sponsor will submit a final study report with the results of the study, including any publications/abstracts of the study, to the accredited METC.

12.6 Public disclosure and publication policy

The study will be registered to a publicly accessible registry and results database (ClinicalTrials.gov). The investigator will submit any proposed publication or presentation along with the respective scientific journal or presentation forum at least 7 days prior to submission of the publication or presentation to all co-investigators.

12.7 Sample destruction after study completion

Any samples left over after analysis will be destroyed when the study is completed. Samples will be discarded in compliance with local biologic waste disposal requirements.

13. STRUCTURED RISK ANALYSIS

Half of the patients who participate in the study will receive standard treatment conform current practice in Radboudumc, HIPEC with flushing afterwards. The other half of the patients will receive standard treatment conform future protocol that will be implemented in the beginning of 2018, HIPEC without flushing afterwards. Because both procedures are currently used in the Netherlands, the additional risk for participation in this study is regarded negligible.

APPENDIX 1: Radboudumc protocol primary HIPEC with oxaliplatin and 5-FU

Checklist kuurnaam/nummer: Primaire HIPEC met oxaliplatin en 5FU

Indicatiegebied: Peritoneale metastasen van colorectale carcinomen, appendixcarcinomen, recidief na primaire HIPEC

Contra-indicaties:

Beenmergdepressie bij begin van de eerste kuur, gedefinieerd als neutrofiele granulocyten $< 2 \times 10^9/l$ en/of trombocyten $< 100 \times 10^9/l$. Perifere sensitieve neuropathie met functieverlies bij aanvang van de eerste kuur. Ernstige nierinsufficiëntie (creatinineklaring $< 30 \text{ ml/min}$). Ernstige leverfunctiestoornissen. Bewezen DPD-deficiëntie.

Kuur medicatie:

Geneesmiddel	Dagdosis	Dag	cyclusduur	Toedieningswijze
Oxaliplatin	460 mg/m ²	1	eenmalig	i.p. opgelost in minimaal volume glucose 5% (max. concentratie 2mg/ml)
Folinezuur	20 mg/m ²	1	Eenmalig	i.v. opgelost in 100 ml NaCl 0,9%
5FU	400 mg/m ²	1	Eenmalig	i.v. opgelost in 50 ml NaCl 0,9% in 4 minuten

Anti-emetica:

Schema 2	Dag 1	Dag 2-3	Dag 4
	Dexamethason 1 dd 8 mg	Dexamethason 1 dd 8mg	geen
	Ondansetron 1 dd 8 mg		

Standaard laboratorium onderzoek:

Vooraf aan start behandeling	Smartset A
------------------------------	------------

Toxiciteit:

5FU: hand-voet syndroom, diarree, reversibele hyperbilirubinemie (meestal indirecte fractie), en minder frequent beenmergsuppressie, alopecia, misselijkheid, braken.

Oxaliplatin: (meestal) reversibele sensibele neuropathie, beenmergsuppressie, misselijkheid, braken, diarree, stomatitis, zelden allergische reacties.

Auteur: [name] Eigenaar: afd medische oncologie	Publicatiedatum: juni 2014 Herzien voor: 23 januari 2017 Versie 3.0: 04-11-2015	Pagina 1 van 3
---	---	----------------

Bijzonderheden:

Voorafgaand aan de CRS-HIPEC procedure dienen alle patiënten gezien te zijn door de medisch oncoloog. De medisch oncoloog is verantwoordelijk voor het voorschrijven van de chemotherapie.

Referenties:


Toedieningsschema tweede lijns HIPEC

Starttijd lijn 1		Medicatie	Dosering protocol	Route	Oplosmiddel	Inlooptijd
00:00		Dexamethason Samen met ondansetron	8 mg + 8mg	i.v.	50 ml NaCl 0.9%	00:15
00:30		folinezuur	20mg/m2	i.v.	100 ml NaCl 0.9%	00:30
01:00		5-fluorouracil	400mg/m2	i.v.	50 ml NaCl 0.9%	01:00
	Starttijd lijn 2 (IP)					
	02:00	Oxaliplatin	460mg/m2	i.p.	Glucose 5% eindconcentratie 2 mg/ml – minimaal volume	01:30

*PAS OP voor i.p. lijn voor en naspoelen met glucose 5% - oxaliplatin is onverenigbaar met NaCl 0,9%

Eerste lijns HIPEC : Oxaliplatin

De spoeling met Oxaliplatin wordt gecombineerd met peroperatieve systemische chemotherapie met Leucovorin (Folinezuur) en 5-FU (cytostaticum). De Leucovorin wordt 1 ½ uur voor spoeling intraveneus toegediend in een dosis van 20 mg/m² in 30 minuten. De 5-FU wordt 1 uur voor het begin van de spoeling i.v. toegediend in een dosis van 400 mg/m² 250 ml NaCl 0,9% in 1 uur. (Leucovorin/ 5-FU: actie anesthesie).

- Het abdomen wordt vanuit de machine gevuld met 5% glucose oplossing. Hieraan toevoegen 2500 i.e. heparine. Oxaliplatin wordt door de apotheek aangeleverd in een infuuszak van 300-500 ml fysiologisch zout. Deze infuuszak wordt aangesloten op het reservoir van de spoelset. Toevoeging van de intraperitoneale Oxaliplatin kan starten wanneer de i.v. chemotherapie volledig is toegediend en de perfusievloeistof een temperatuur van 41-42° C heeft bereikt. De totale dosis van 460 mg/m² wordt in één gift toegevoegd. De totale duur van de spoeling is 30 minuten (i.t.t. mitomycine (=90 minuten))

Tweede lijns HIPEC : Mitomycine C

Tweede lijns HIPEC met mitomycine C wordt gegeven als patiënt na CR en HIPEC met Oxaliplatin voor een recidief behandeld wordt met CR en HIPEC. Het HIPEC systeem wordt gevuld met dialyse vloeistof (Physioneal) , 2500 i.e. heparine en 10 ml KCl 7.5% en opgewarmd tot 43° C. Na aansluiten via de drains op de buikholte , deze opwarmen tot 42° C.

De Mitomycine C wordt toegevoegd aan de dialyse vloeistof als de juiste temperaturen zijn bereikt. Er wordt 90 minuten geperfundeerd met chemotherapie.

- Mitomycine C dosering : 35 mg/ m² lichaams oppervlak. Te verdelen over 3 doseringen. De maximale dosering gaat uit van een lichaamsoppervlak van 2 m². Dus bij een patiënt met een groter lichaamsoppervlak dan 2 m² wordt maximaal 70 mg in 3 dosis gegeven.
- De totale dosis wordt verdeeld over 3 injectiespuiten die door de apotheek worden klaargemaakt:
 - 1^e gift : 50% van de totale dosis Mitomycine C wordt gegeven als de temperatuur in de buikholte 42° C is.
 - 2^e gift : 25% van de totale dosis Mitomycine C wordt gegeven 30 minuten na de eerste gift.
 - 3^e gift : 25% van de totale dosis Mitomycine C wordt gegeven 60 minuten na de eerste gift.

Bij huidcontact met een van boven genoemde cytostatica : spoelen met (veel) kraanwater.

Per oktober 2014 is 1^e lijns medicatie Oxaliplatin geworden i.p.v. Mitomycine C

Bron : Protocol HIPEC (OK)

5 november 2015

HIPEC

Werkinstructie, OK Heelkunde (HEELK)

Indicatie ingreep

Patiënt met carcinosis peritonei op basis van colorectaal carcinoom of pseudomyxoma peritonei of mesothelioom. Er vindt preoperatief een selectie plaats en patiënt stemt in met Hipec ingreep. Patiënt krijgt bij sommige protocollen oxaliplatin of cisplatinum+doxorubicine of Mitomycine C.

Controleer aan het begin van de dag. Alle chemotherapie moet met de patiënt meekomen vanaf de afdeling. Chemo wordt kant en klaar geleverd door de apotheek in een grijze chemokist. Deze kist hoort met de patient mee te komen van de verpleegafdeling naar de operatiekamer. Als deze niet op het bed aanwezig bij aankomst van de patient op de OK, checken bij de verpleegafdeling ([name]), anders navragen bij de apotheek. Controleer de houdbaarheid van alle cytostatica. **Tijdstip houdbaarheid chemo doorgeven bij time out en opschrijven op het bord.**

Ligging patiënt

Op de operatietafel komt op een saharalaken te liggen. Patiënt heeft steunkousen aan. Patient wordt nadat de epiduraal catheter, een lieslijn en een centraal veneuze lijn heeft gekregen in de beensteunen gelegd. De diathermieplaat wordt dwars op het rechter bovenbeen geplaatst zodat de klip net niet onder de kous valt en naar beneden kan wegklappen. Op de diathermie plaat wordt de lieslijn bevestigd.

Zie voor algemene informatie: [Positionering van de patiënt op de operatietafel](#)

Desinfecteren

Patiënt desinfecteren vanaf tepellijn tot os pubis. Perineum poetsen met chloorhexidine. Bij vrouw ook een vaginaal toilet met betadine jodium.

Afdekken

Alle afdekmaterialen gebruiken van de firma Medline. Zijdoekje onder de stuit plaatsen. Twee zijdoekjes aanbrengen. Per been wordt een groot laken over het been gedrapeerd. Groot laken vanaf tepels naar boven plaatsen. opvangzakje plaatsen onder de anus. Ioban steridrape over buik plaatsen. Deze beide zijn bedoeld om eventueel druppen tijdens spoelen op de grond te voorkomen.

Extra benodigdheden

Bij toepassing van oxaliplatin de dag vantevoren 6 stuks Glucose 5% 1000ml infusievloeistof klaarleggen in de warmtekast. Bij de toepassing van Mitomycine C wordt de dag van tevoren Physioneal 35 van Baxter klaargelegd.

Zorg ervoor dat er voldoende NaCl spoelvloeistof klaarligt.

Hipec aandachtspunten

Bij een Hipec zorg je ervoor dat alle spullen die nodig zijn tijdens het spoelen al op de ok liggen tijdens de debulking. De hipec-brillen, schoenhoezen, maskers, jassen, celstofmatjes en groene matten op de ok plaatsen.

Oxaliplatinprotocol: Er wordt gestart met de debulking zonder gebruik te maken van chemostaticca. Tijdens deze fase geen extra beschermende maatregelen.

In overleg met de operateur wordt er gestart Folinaat (Leucovorin 20 mg/m²) in 100 ml NACL 0,9%. Dit loopt intraveneus in 30 minuten in. Dit is foliumzuur en is dus nog geen chemo,(dit heet ook Rescuvolin 5 ml = 50 mg) ligt in koelkast in anaesthesieruimte.

In overleg met de operateur wordt er gestart met intraveneuze chemo. Fluouracil (5FU 400 mg/m²) in 250 ml NACL 0,9% wordt aangesloten en zal in 60 minuten inlopen. Daarna het infuus doorspoelen met NACL.

Hierna kan er gestart worden met de peritoneale perfusie.

Het abdomen wordt gevuld met Glucose oplossing. Toediening van de Oxaliplatin kan starten wanneer de i.v. chemotherapie volledig is toegediend en de perfusievloeistof een temperatuur heeft bereikt van 42-43°C. Het spoelen met Oxaliplatin duurt 30 minuten.

Vanaf het inspuiten of het lopen van het perfusaat met chemo worden de preventieve absorberende onderleggers geplaatst. Het opererend team trekt reinforced jassen en dubbele Biogel handschoenen aan. De omloop trekt de blauwe omloopjas, bril en eventueel de schoenhoezen aan.

De instrumenterende gaat vanaf het inlopen van de Fluouracil of na het begin van het spoelen van de buik met chemo de gazen als besmet beschouwen en verzamelt alle gazen in een grote kom.

Mitomycine C protocol: toediening in perfusievloeistof in drie giften toegevoegd aan het perfusaat, perfusie gedurende 90 minuten.

Cisplatinum+doxorubicine protocol: volgens instructie van de operateur

Perfusionist werkt bij de Hipec met het Medtronic gemodificeerde heater/cooler. Je gebruikt dan dus ook de Medtronic hipec kit.

De perfusionist heeft ongeveer 45 minuten nodig voor aanvang van het peritoneal spoelen zodat het apparaat opgebouwd kan worden en de vloeistof opgewarmd kan worden.

Risico en bescherming:

Blootstelling aan cytostatica wordt voorkomen door het nemen van de juiste veiligheidsmaatregelen. Het belangrijkste gevaar is besmetting van het cytostaticum door huid of oogcontact (direct of door beschadiging/perforatie van handschoenen, kleding of oogbescherming of door spatten of morsen) of accidenteel inslikken (bijvoorbeeld via besmette handen)

Beschermende maatregelen:

Saharamat op de ok tafel

Voor aanvang cytostatica bordjes op ok deur.

Beschermende bril (3M)

Mondmasker, elk mondmasker is afdoende, de cytostatica kent geen dampfase en zal zich dus niet in de lucht bevinden.

Impermeabele (reinforced) ok jas

Eventueel schoenhoezen

dubbele latexhoudende Biogel handschoenen tijdens en na het spoelen. Bij spoelen over de dubbele handschoenen de lange ellebooghandschoenen dragen om lekkage via de manchetten te voorkomen. Is de patiënt overgevoelig voor latex dan biogel underglove (blauwe handschoen) en daaroverheen biogel skinsense.

Waterafstotend afdekmaterial

Plastic kap boven buikholte om spatten te voorkomen

Preventieve absorberende onderleggers op de grond

Afvalcontainers voor afval die geproduceerd wordt na het spoelen met cytostatica

Na de ok de spatzone poetsen met disposable poetsdoeken, deze na gebruik weggooien in de risicoton.

Instrumentensets gaan in instrumentenkar, deze worden door operatie-assistenten afgevoerd naar de vuile dienst.

Veegproeven incidenteel (ongeveer 1x per jaar) en als hier aanleiding voor is

Handelen bij calamiteiten

Bij huidcontact: spoelen met veel (kraan) water

Bij oogbesmetting: oog spoelen met oogdouche

Zie acute koffer.

Instrumentarium

Als de instrumenterende links staat.

Van linksonder naar rechtsonder:

- Mes 20, twee gilles pincetten, mayo schaar, metzembau schaar kort en lang, debakey kort en lang, 2 lang chirurgische pincetten, 8 crile klemmen en 2 kochers.

Rechtsmidden:

- Gazen

Linksmidden:

- Naaldvoerders lang en kort

Van linksboven naar rechtsboven:

- Monihan fijn en groot, heiss klem kort en lang, mitteldorp haken en scherpe haken.

Verloop ingreep

Cytoreductieve chirurgie. Hierbij is het doel om zoveel mogelijk te verwijderen van macroscopische tumordeposities van het viscerale en parietale peritoneum, zonodig met multiviscerale resectie. Dit is per patiënt erg verschillend.

Tijdens vooraf aan de debulking worden voorbereidingen gemaakt voor het spoelen. nl: Ok assistent bevestigt op twee plaatsen 4 thermometers aan 4 Abdovac FG 18 met vicryl 2. De thermometers steken ietsje uit tov de drains. Op de outflowdrain wordt de dreesman zuiger geplaatst nadat de gaten van de drain zijn afgeknipt. De outflowdrain en de temperatuurmeters worden na het spoelen verwijderd uit de buik. Chirurg hangt de buikwand op met doekklemmen en tie-wraps aan de Booklerspreider. Hierdoor wordt de buik omhooggespannen en kun je een diepere holte creëren. De temperatuursondes worden aangesloten op temperatuurmeter van het perfusieapparaat. Deze temperatuurmeter inpakken in een steriel camerahoes. Via de slangenset worden de invoerdrains aangesloten op het perfusieapparaat. Bij de slangenset de invoerregelaars opschuiven naar de plaats waar de connectie wordt gemaakt. Er wordt gekeken of de drains op de goede plaats liggen. Aan de hand van de temperatuurmeting wordt gekeken of er een goede invoer van vloeistof is in de buik. De uitvoerslang wordt ook bevestigd aan het perfusieapparaat. Er wordt een hoes aangebracht over de spreider, dit om spatten te voorkomen.

Bij start van de Oxiplatin of Mitomycine C verdwijnen er zoveel mogelijk mensen uit de ok. De pa-preparaten worden ingestuurd. De anaesthesist of anaesthesie-assistent blijft op de ok. De perfusionist bedient het apparaat. De operateur komt roeren in de buik van de patiënt. Het spoelen duurt 30 minuten.

Beschermende maatregelen: spatbril, jas, slippers, masker en dubbele biogel handschoen met daaroverheen ellebooghandschoenen. Tijdens het spoelen wordt het gebruikte instrumentarium in een kom met H2O gelegd.

Na het spoelen volgt eventueel de reconstructie door een darmnaad of een anus preaternalis aan te leggen. Daarna wordt de fascie gesloten, de huid wordt gesloten met huidnietjes.

De drainflessen worden zorgvuldig bevestigd aan de drainpotten. Deze drainopeningen netjes afplakken met hansapor en grip lok.

Bij de hipec worden aan het eind van ingreep alle instrumenten in een instrumentenkar geplaatst. Deze kar plaatsen in de vuile ruimte.

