7. NON-INVESTIGATIONAL PRODUCT

Cytoreductive surgery combined with HIPEC is performed according to local standard treatment (APPENDIX 1). One and a half hour before the intraperitoneal administration of oxaliplatin, the patient is treated with an intravenous infusion of folic acid in a dose of $20\text{mg}/\text{m}^2$ administered over 30 minutes. One hour prior to the beginning of IPCH the patient is treated with 5-FU in a dose of $400\text{mg}/\text{m}^2$ administered in 60 minutes to augment the effects of hyperthermic intraperitoneal oxaliplatin. According to local protocol HIPEC is performed using an open abdominal cavity procedure with the skin pulled upwards (coliseum technique). The abdominal cavity is filled with 5% dextrose. 2500IU of heparin are added to this solution. After 5-FU is administered and the instillate solution has reached a temperature of $41\text{-}42\text{ }^\circ\text{C}$, oxaliplatin is administered in a dose of $460\text{ mg}/\text{m}^2$. Oxaliplatin is delivered by the pharmacy in a 5% dextrose solution in the exact dose required for the patient in a concentration of 2mg/ml. Duration of IPCH is 30 minutes.

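### Appendix 1 contradicts itself and Section 7 on the intravenous drugs before HIPEC: 5-FU over 4 or 60 minutes, diluent 50 or 250 ml, folate called folic or folinic acid

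*Protocol*

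**What the plan says.** Sections 5.1 and 7 both say that surgery and HIPEC follow the local standard in Appendix 1. That appendix combines a chemotherapy checklist, an administration schedule, a text on first-line oxaliplatin and a theatre work instruction, all in Dutch.

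**5-FU, 400 mg/m²**
- Appendix 1, medication table: "i.v. opgelost in 50 ml NaCl 0,9% in 4 minuten" (dissolved in 50 ml saline, over 4 minutes).
- Appendix 1, administration schedule: "50 ml NaCl 0.9% 01:00" (50 ml, run time one hour).
- Appendix 1, first-line oxaliplatin text: "250 ml NaCl 0,9% in 1 uur" (250 ml, one hour).
- Appendix 1, work instruction, oxaliplatin protocol: "in 250 ml NACL 0,9% wordt aangesloten en zal in 60 minuten inlopen" (250 ml, 60 minutes).
- Section 7: "administered in 60 minutes to augment the effects of hyperthermic intraperitoneal oxaliplatin", with no volume.

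**Folate, 20 mg/m²**
- Section 7: "the patient is treated with an intravenous infusion of folic acid in a dose of" 20 mg/m². Section 1 also says folic acid.
- Appendix 1, medication table and schedule: Folinezuur (folinic acid). The first-line text has "Leucovorin (Folinezuur) en 5-FU (cytostaticum".
- Appendix 1, work instruction: names the product as folinate and Leucovorin, then explains it with "Dit is foliumzuur en is dus nog geen chemo", where foliumzuur is the Dutch for folic acid.

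**The concern.** Someone who takes the intravenous part of the regimen from this protocol finds two infusion times and two diluent volumes for the same cytotoxic dose. They also find two names for the drug that precedes it, and folic acid and folinic acid are different substances.

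The text carries weight because Sections 5.1 and 7 make Appendix 1 the treatment description. The statement that participation adds negligible risk (Summary and Section 11.4) also rests on patients receiving that standard treatment. If the standard is written in conflicting ways, the protocol does not define one background regimen for its 20 patients. A 15-fold conflict in the rate of an intravenous cytotoxic is a safety matter in itself, whatever its bearing on the endpoints.

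**Working it through.** The plan has no figure to reproduce here. The check sets the statements side by side and adds simple division.

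| Place | 5-FU time | Diluent | Folate name |
|---|---|---|---|
| Section 1 | not stated | not stated | folic acid |
| Section 7 | 60 min | not stated | folic acid |
| App. 1, medication table | 4 min | 50 ml | folinic acid |
| App. 1, schedule | 1 h | 50 ml | folinic acid |
| App. 1, first-line text | 1 h | 250 ml | Leucovorin (folinic acid) |
| App. 1, work instruction | 60 min | 250 ml | folinate/Leucovorin, then folic acid |

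The 5-FU dose is 400 mg/m² in every row except Section 1, which gives a background range of 400–450 mg/m². The folate dose is 20 mg/m² throughout.

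**Dose rate of 5-FU** = dose / time
- 4 minutes: 400 / 4 = 100 mg/m² per minute.
- 60 minutes: 400 / 60 = 6.67 mg/m² per minute.
- Ratio: 60 / 4 = 15. Body surface area cancels, so no assumption about it is needed.

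**Diluent volume:** 250 / 50 = 5.

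**Fluid rate** = volume / time, for the three combinations that the appendix contains
- 50 ml in 4 minutes: 50 / 4 = 12.5 ml/min.
- 50 ml in 60 minutes: 50 / 60 = 0.83 ml/min.
- 250 ml in 60 minutes: 250 / 60 = 4.17 ml/min.

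**How the statements divide**
- On time, one statement gives 4 minutes and four give 60 minutes or one hour.
- On volume, there are two statements each way, all inside Appendix 1.
- On the folate, the English body and the Dutch appendix differ, and the work instruction uses both names.
- The schedule has a further problem: it is headed as second-line HIPEC but lists oxaliplatin, while the same appendix describes second-line HIPEC as mitomycin C. Its heading and contents therefore disagree about which regimen it governs.

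**The case against.** The other side has a good deal to say.

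**Weight of the text.** Section 7 is clear on duration, and three parts of Appendix 1 agree with it. The 4-minute entry stands alone, so the two times do not have equal support, and it would be too strong to say that the regimen cannot be followed. That stands. The count does not resolve the conflict, however. The 4-minute entry is in the medication table of a checklist owned by medical oncology, and that checklist makes the medical oncologist responsible for prescribing. The hour-long infusion in the first-line text is assigned to anaesthesia. So a prescribing document and administration instructions disagree. The checklist was also due for revision before 23 January 2017, while the study was expected to start in November 2017.

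**Routine care.** 5-FU and folate are not investigational, and the pharmacy delivers the chemotherapy ready for use, so volume is largely a preparation detail. This lowers the chance that a patient is affected. It does not make the protocol's own treatment description consistent.

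**The folate.** Appendix 1 names folinic acid or Leucovorin repeatedly, and folic acid in the work instruction is a gloss for theatre staff. This may be only a slip in naming. Nothing shows that a different product is supplied. The names still conflict.

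**Timing.** A reader might infer that, on the 4-minute reading, 5-FU ends 56 minutes before oxaliplatin (60 − 4). The documents do not support this. The medication table gives no start time, and the one-hour lead in Section 7 and the first-line text belongs to a one-hour infusion. Oxaliplatin also waits for completion of 5-FU and for perfusate temperature, so a short infusion need not leave such a gap.

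**Trial results.** A reader might also infer bias between the consecutive flushing and non-flushing groups, or in the primary endpoint. Neither is shown. 5-FU precedes both tissue samples in each pair, it is not measured, and the protocol nowhere says that its infusion rate changes platinum concentrations. The only difference stated between the groups is flushing.

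**Conclusion.** The point holds as a contradiction in the treatment description and must be corrected. For one 400 mg/m² dose of 5-FU the documents give infusion times that differ 15-fold in rate. Appendix 1 gives diluent volumes that differ 5-fold, and the folate carries two names. The ratios follow directly from the stated figures and rest on no assumption about patients.

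The matter is one of treatment consistency and patient safety. It does not extend to the primary within-patient platinum comparison or to the comparison of the two groups, and no misadministration is shown. The volume conflict lies wholly within Appendix 1. The documents do not settle which time, volume or folate name applies, and this review takes no position on that.

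**What to change.** Reconcile Section 1 (folate name), Section 7 and the four parts of Appendix 1 (medication table, schedule, first-line oxaliplatin text, work instruction). They should state one 5-FU infusion time, one diluent volume and one named folate product, as decided by the treating team and pharmacy. Correct the mismatch between the schedule's second-line heading and its oxaliplatin contents in the same pass, so that it is clear which regimen it governs.

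The cost is a document correction after a check with medical oncology, anaesthesia and the pharmacy. Sample size, sampling and analysis do not change. No additional data collection is needed for this point, since 5-FU timing enters no planned analysis.

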5. TREATMENT OF SUBJECTS

5.1 Investigational product/treatment

Cytoreductive surgery combined with HIPEC is performed according to local standard treatment (APPENDIX 1).

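### Appendix 1 contradicts itself and Section 7 on the fluid of the pharmacy bag that holds the full oxaliplatin dose: physiological saline in one sentence, glucose/dextrose 5% elsewhere, with a footnote calling oxaliplatin incompatible with NaCl 0.9%

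*Protocol*

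**What the plan says.** Section 5.1 consists of a single reference: "Cytoreductive surgery combined with HIPEC is performed according to local standard treatment (APPENDIX 1". Section 7 repeats it and then gives its own English description, which includes "Oxaliplatin is delivered by the pharmacy in a 5% dextrose solution" at 2 mg/ml. Nothing in the protocol says which text prevails if the two differ.

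Appendix 1 reproduces several Dutch hospital texts. Four places in it bear on the bag fluid:

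- Medication table (Kuur medicatie), oxaliplatin row: "i.p. opgelost in minimaal volume glucose 5% (max. concentratie 2mg/ml", that is, dissolved in a minimal volume of glucose 5%.
- Administration schedule (Toedieningsschema), oxaliplatin row: "Glucose 5% eindconcentratie 2 mg/ml".
- Footnote to that schedule, on flushing the intraperitoneal line with glucose 5%: "oxaliplatin is onverenigbaar met NaCl 0,9", that is, oxaliplatin is incompatible with NaCl 0.9%.
- First-line text (Eerste lijns HIPEC: Oxaliplatin): "Oxaliplatin wordt door de apotheek aangeleverd in een infuuszak van 300-500 ml fysiologisch zout", that is, the pharmacy supplies oxaliplatin in a 300-500 ml bag of physiological saline. The bag is connected to the reservoir, and the total dose "wordt in één gift toegevoegd" (is added in one go).

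**The concern.** One sentence of the operative treatment text names, for the whole cytotoxic dose, a fluid that a footnote in the same appendix calls incompatible with the drug. Section 7 and two tables name another. A reader who follows the references in Sections 5.1 and 7 meets both statements and has no rule for choosing between them.

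What is at stake is the safety and clarity of the document. An approved protocol should not carry a statement about the full dose that its own warning contradicts. The statistical analysis does not enter into it, and an analysis plan would not settle it.

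**Working it through.** The protocol states no figure to reproduce here. The check sets the places side by side and adds one calculation.

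**Bag fluid**

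| Place | Fluid |
|---|---|
| Section 7 | dextrose 5%, 2 mg/ml |
| Appendix 1, medication table | glucose 5%, at most 2 mg/ml |
| Appendix 1, administration schedule | glucose 5%, 2 mg/ml |
| Appendix 1, first-line text | physiological saline, 300-500 ml |
| Appendix 1, schedule footnote | oxaliplatin incompatible with NaCl 0.9% |

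The sentences are complete, so this is not a redaction or a fault of text extraction.

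**Could these be two different products?** Inputs: dose 460 mg/m² and concentration 2 mg/ml (Section 7 and the schedule), and bag volume 300-500 ml (first-line text).

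- Bag volume = 460 × BSA / 2, so BSA = 2 × volume / 460.
- 300 ml: 2 × 300 / 460 = 1.30 m².
- 500 ml: 2 × 500 / 460 = 2.17 m².
- For an assumed BSA of 1.8 m²: 460 × 1.8 = 828 mg, and 828 / 2 = 414 ml.

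The volume range given for the saline bag is what the 2 mg/ml solution needs for a BSA of 1.30-2.17 m². This fits one pharmacy bag described with two fluids. It does not show which fluid is meant.

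**What is not in conflict.** The fluid that fills the abdomen is glucose or dextrose in Section 7, in the first-line text and in the work instruction. The sodium chloride flush in Section 3 and Appendix 3 is a separate step after the instillate has been evacuated.

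**Smaller disagreements found in the same comparison**

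| Item | One statement | Other statement |
|---|---|---|
| Oxaliplatin time | 01:30 run-in = 90 min (schedule) | 30 min perfusion (Summary, Sections 1 and 7, first-line text, work instruction) |
| Heading of the oxaliplatin schedule | second-line HIPEC | second line is mitomycin C (Appendix 1 text) |
| 5-FU infusion time | 4 min (medication table) | 60 min (Section 7, schedule, first-line text, work instruction) |
| 5-FU volume | 50 ml (medication table, schedule) | 250 ml (first-line text, work instruction) |
| 5-FU dose | 400-450 mg/m² (Section 1) | 400 mg/m² (Section 7 and Appendix 1) |
| Temperature for adding oxaliplatin | 41-42 °C (Section 7, first-line text) | 42-43 °C (work instruction) |
| Co-drug at 20 mg/m² | folic acid (Sections 1 and 7) | folinic acid/leucovorin (medication table, schedule, first-line text); both names (work instruction) |

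Two cautions apply. The schedule's 90 minutes is a run-in time and the 30 minutes is a perfusion time. They do not fit together, but they are not one quantity. The 43 °C perfusion temperature in the Summary and Section 1 may differ in kind from the temperature at which drug is added, so it is not counted here.

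**The case against.** The strongest reply is that this is one wording conflict in a reproduced hospital text. Oxaliplatin HIPEC is routine care here, not a study product. Section 7 gives one clear fluid, and the oncology checklist, whose medication table agrees with it, makes the medical oncologist responsible for prescribing. The work instruction adds "Chemo wordt kant en klaar geleverd door de apotheek" (chemotherapy comes ready-made from the pharmacy), so operating-room staff do not choose the fluid. The bag volume fits the 2 mg/ml solution, so only the name of the fluid differs.

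Much of this stands, and it lowers the likelihood of harm. It does not remove the conflict. The saline sentence is itself a statement of what the pharmacy delivers, so ready-made delivery does not settle which fluid is meant. Sections 5.1 and 7 make the appendix part of the treatment description, so it cannot be set aside as background. Nor does the schedule's second-line heading confine the footnote to another drug: the schedule lists oxaliplatin 460 mg/m² intraperitoneally.

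A reader might go further in four ways that the documents do not support:

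- *That patients receive the drug in saline.* Nothing shows that the sentence is followed.
- *That platinum levels, or the before-and-after flushing comparison, are affected.* The documents give no basis for deriving such an effect.
- *That the whole perfusion is in doubt.* The abdominal fill is not in conflict.
- *That the saline sentence was overdue for revision, because Appendix 1 shows a revise-by date of 23 January 2017 and the study was to start in November 2017.* That date belongs to the oncology checklist, whose own table says glucose 5%. The section with the saline sentence names the operating-room HIPEC protocol as its source.

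**Conclusion.** The contradiction is real and must be removed before the first patient. One statement of saline stands against three of glucose or dextrose 5%, it concerns the whole 460 mg/m² dose, and a footnote in the same appendix calls the drug incompatible with NaCl 0.9%.

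The priority rests on that conflict alone. The items in the second table are minor document corrections and do not raise it. The conclusion depends on reading Appendix 1 as operative text, which Sections 5.1 and 7 support. It needs no assumption about practice on the ward or in the pharmacy. The BSA calculation is supporting only, and the conclusion would stand without it.

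**What to change.** Before the first patient, the sponsor, pharmacy and treating team must reconcile Section 7 with the Appendix 1 medication table, administration schedule, footnote and first-line text, so that the bag fluid is stated once and identically. Which fluid is right is for them to decide.

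In the same edit, they should bring each smaller item in the second table to a single statement: the oxaliplatin run-in and perfusion time, the schedule heading, the 5-FU infusion time, volume and dose, the temperature for adding oxaliplatin, and the name of the 20 mg/m² co-drug. The edit must include Section 1; otherwise the 5-FU dose range and the co-drug name there would not be settled.

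The cost is a text correction of the protocol and Appendix 1, with any revision of the reproduced hospital documents made by their owners. It adds no patients, samples or procedures.
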